3.4 Estimated Accrual

We estimate that we will enroll approximately 30 patients per year, to complete accrual in 5 years.

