17.2 Primary/Secondary Endpoints, Objectives and Analytical Methods

The primary endpoint of the study is overall survival from the time of randomization. The survival (in days) of subjects in the two arms will be compared using the stratified log-rank test (stratified on number of chemotherapy cycles and disease risk, factors that randomization is stratified on). Patients still alive at last contact will be censored. End of study will be defined as 2 years after the last patient is randomized. The primary endpoint will be compared between groups using the intent-to-treat principle.

A secondary endpoint of the study is **relapse-free survival** (RFS) from the time of randomization, to be compared between groups with the stratified log-rank test. For descriptive purposes, we shall also report survival and RFS estimates from time of transplant among patients who receive a transplant. Patients alive without relapse at last contact will be censored for RFS.

[figure not shown]
A secondary objective of the study is to compare the **rate of transplantation** among patients with MRD following intensive chemotherapy. The proportion of patients who were transplanted will be compared between arms using the chi-square test

A secondary objective of the study is to examine the **types of transplant** received following treatment with CPX-351 as compared to patients receiving immediate transplantation. Among patients receiving transplantation, the proportion of patients in each arm receiving myeloablative transplant conditioning will be compared using the chi-square or Fisher's exact test. Among patients receiving transplantation, the proportion of receiving donor stem cells from a haploidentical donor, an unrelated donor, or from cord blood unit will be compared across arms using the chi-square or Fisher's exact test.

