17.3 Sample Size and Power

Outcomes for patients with MRD following intensive chemotherapy at FHCRC since 2008 were reviewed. From these observed data, we fit piecewise exponential survival distributions and used these as the assumed-true distributions for the two arms. These assumed-true distributions are shown

in the figure below. From the observed data, the hazard of death was estimated to be 0.58 (transplant vs chemotherapy).

Estimates of power for specified sample sizes were obtained by randomly drawing survival times from each assumed-true survival distribution for the number of patients assumed for each group, resulting in “simulated” clinical trials under the assumptions depicted in the curves above. The data from this simulated trial were then compared using the log-rank test and a p-value was generated. This process was repeated 500 times, and the proportion of simulated trials that led to a p-value less than the significance level dictated by the trial provides an estimate of power to observe a statistically significant (at a two-sided significance level) difference in survival between the two groups.

Power estimates further assumed uniform accrual over 3 years with minimum follow-up of 2 years (so the longest potential follow-up would be 5 years and the minimum potential follow-up would be 2 years).

Based on the assumptions above, the estimated power for this design is summarized below for various significance levels and 65 patients/group. Power estimated from 500 simulations. The number of events required is estimated to be 107.

Alpha=.05, power ~ 89.4%

Alpha=.10, power ~ 93.8%

Alpha=.15, power ~ 94.8%

Alpha=.20, power ~ 96.4%

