17.5 Study-suspension Rules and Interim Futility Analysis

As noted above in section 11, the CPX arm will be followed carefully for toxicity and the inability for patients treated with CPX to proceed to HCT or be delayed to HCT (defined as start of transplant conditioning regimen more than 60 days following the start of CPX; inability to receive HCT or a delayed HCT is defined below as “failure”) due to toxicity attributable to CPX. Toxicity attributable to CPX will be defined as any adverse event that is possibly, probably, or definitely related to CPX. Events that do not meet this definition but result in the delay of HCT or inability to proceed to HCT (e.g.

treating clinic logistics, scheduling, donor availability, unrelated adverse events) will not count toward study-suspension rules but will be captured as protocol deviations in the study records. In situations where HCT is delayed or patient is unable to proceed due to toxicity and attribution to CPX is unclear, the DSMB will be consulted.

If toxicity from CPX leads to an observed failure rate of 20% or more, the study will be suspended pending review by the DSMB. This assessment will be made after every 5th enrolled patient, so any of the following would trigger this suspension rule: 1 of 5 or fewer, 2 of 10 or fewer, 3 of 15 or fewer, 4 of 20 or fewer, 5 of 25 or fewer, 6 of 30 or fewer, 7 of 35 or fewer, 8 of 40 or fewer, 9 of 45 or fewer, 10 of 50 or fewer, 11 of 55 or fewer, 12 of 60 or fewer, or 13 of 65 or fewer patients experience a failure.

After 65 patients have been enrolled and minimum follow-up reaches 6 months, the conditional power (given results up to this point) to reach a statistically significant difference at the end of the study will be calculated under the assumptions (for patients to be enrolled in the future) used in the initial power calculations. If this conditional power is less than 20%, consideration will be given to terminating the study due to futility. Other considerations will go into this decision (not just the conditional power) and presented to the DSMB, but this will be a large driver of the ultimate decision. Accrual to the study will not be suspended while the interim analysis is being conducted.

**Projected Target Accrual
ETHNIC AND GENDER DISTRIBUTION CHART**

TARGETED / PLANNED ENROLLMENT: 130			
Ethnic Category	Sex / Gender		
	Females	Males	Total
Hispanic or Latino	1	3	4
Not Hispanic or Latino	55	71	126
Ethnic Category Total of All Subjects*	56	74	130

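### Section 17.5's only between-arm survival look states a futility number that rises from no difference through harm to Arm B, with no survival-harm level beside it; adding a DSMB-review pause is a cheap improvement

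*Combined protocol and SAP*

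**What the plan says.** Section 17.5 calls for "the conditional power (given results up to this point) to reach a statistically significant difference at the end of the study", computed once 65 patients are enrolled and minimum follow-up is 6 months, with patients yet to be enrolled following the assumptions of the power calculation. The guideline is "If this conditional power is less than 20%, consideration will be given to terminating the study due to futility". The section adds "Other considerations will go into this decision (not just the conditional power) and presented to the DSMB", but also that "this will be a large driver of the ultimate decision". It also says "Accrual to the study will not be suspended while the interim analysis is being conducted".

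The design assumptions are in Section 17.3: "the hazard of death was estimated to be 0.58 (transplant vs chemotherapy". Inverted, the Arm B versus Arm A hazard ratio is 1/0.58 = 1.72, so Arm B is assumed to do worse. Section 17.2 makes the primary test a two-arm log-rank test "stratified on number of chemotherapy cycles and disease risk".

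Other oversight exists:
- Section 17.5 suspends the study if 20% or more of CPX-351 patients miss or are late for transplant because of CPX-attributed toxicity, checked after every fifth patient.
- Section 4.1 lets the investigator stop for low accrual or infrequent transplantation after CPX-351, and Section 20.0 for any reason.
- Section 11.1 has weekly review of every patient's course, Section 9.4 regular review of post-transplant data, and Section 15.0 committee review at least annually.
- Sections 12.0 and 14.4 keep survival follow-up and death reporting going after treatment stops.

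None of these gives a hazard ratio, test statistic, p-value or death count for worse survival on one arm.

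**The concern.** Worse survival with chemotherapy first is the difference that the trial is powered to detect, and Section 2.2.3 reports retrospective local data pointing the same way. If it appears by the interim, the one number promised to the DSMB moves away from its threshold. A high conditional power then reads as a reason to continue, although it is high because Arm B patients are dying faster. The other suspension rule would not necessarily respond: it counts only transplants lost or delayed through CPX-attributed toxicity, so relapse during the delay, unrelated deaths and post-transplant deaths fall outside it. At stake are the Arm B assignments still to be made after the look.

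**Working it through.** **Inputs from the documents.** Hazard ratio 0.58, 107 deaths, 65 per arm, two-sided test, 3-year accrual plus 2 years of follow-up (17.3). Four alpha levels are listed and none is named as the trial's; .05 is assumed here. Section 3.4 gives a slower pace: "We estimate that we will enroll approximately 30 patients per year, to complete accrual in 5 years"; 130/30 = 4.33 years.

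**The plan's own figure.** The stated power is 89.4% at alpha .05. The drift is ln(1/0.58) × √(107/4) = 0.545 × 5.172 = 2.82, so proportional-hazards power is Φ(2.82 − 1.96) = 80.4%. The 89.4% is not reproduced. It came from piecewise curves in a figure not shown, which need not have proportional hazards, so it is not called wrong. The substitute curves below give 78-80%.

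**Conditional power at 35 deaths.** Let U = ln(observed HR) × 35/4. Of the 72 remaining deaths, 34-42 are taken to occur in patients already enrolled (n_e) and the rest in future patients (n_f). Then:

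- mean of final U = U + (drift for enrolled) × n_e/4 + 0.545 × n_f/4
- SD = √(72/4) = 4.243
- critical value = 1.96 × √(107/4) = 10.137, both tails counted

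Section 17.5 fixes the drift for future patients but not for those already enrolled, so three readings were run.

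*Example, no further difference in enrolled patients, n_e = n_f + 4 = 38, n_f = 34:*
- Observed HR 1.0: mean = 0 + 0 + 0.545 × 8.5 = 4.63; (10.137 − 4.63)/4.243 = 1.30; conditional power about 10%.
- Observed HR 2.0: U = 0.693 × 8.75 = 6.07; mean = 10.70; (10.137 − 10.70)/4.243 = −0.13; about 55%.

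| Drift for enrolled patients | HR 1.0 | HR 1.5 | HR 2.0 | HR 2.5 |
|---|---|---|---|---|
| observed trend continues | 8-12% | 66-68% | 95-96% | >99% |
| no further difference | 8-12% | 28-37% | 50-60% | 68-76% |
| design | 47% | 78% | 91% | 97% |

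Raising the drift to that implied by 89.4% power (3.21) keeps the pattern: at information fraction 0.35, with design drift for all remaining deaths, conditional power is 56% at HR 1.0 and 96% at 2.0.

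The rise does not extend over the whole range. On the trend reading, when Arm B looks much better (observed HR 0.4-0.5), conditional power climbs back to 22-79%.

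**A harm level at the same look.** 4,000 trials were simulated per scenario. Hazards were constant, or twice as high in year 1, and calibrated to 107 deaths with 3-year accrual; accrual took 3 or 4.33 years; stratum effects were absent or assumed (HR 1.75 for risk, 1.25 for cycles). The rule was a stratified log-rank Z above 2.576 against Arm B (one-sided p<0.005).

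| True HR, B vs A | Trials paused |
|---|---|
| 1.0 | about 0.3-0.5% |
| 1.72 | 14-21% |
| 2.0 | 27-37% |
| 2.5 | 55-69% |

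At HR 1.72 the look has about 34-44 deaths, so the pause needs an observed hazard ratio of about exp(2 × 2.576/√44) = 2.17 to exp(2 × 2.576/√34) = 2.42. About 80-87 patients are randomised by then, leaving (130 − 87)/2 to (130 − 80)/2, or 22-25, Arm B assignments. If every pause became permanent, the average avoided is at most 0.14 × 22 = 3 to 0.21 × 25 = 5 at HR 1.72, and 12-17 at HR 2.5.

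Whenever Arm B was worse at p<0.005, conditional power was at least 0.52 at alpha .05 (0.66, 0.74 and 0.79 at .10, .15 and .20) under every reading. The 20% guideline never fired in those trials.

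**The case against.** The strongest reply is that a futility-only look is a legitimate choice. Worse survival with chemotherapy first is the effect that the power calculation assumes. A harm boundary is in effect early stopping for the primary result, at roughly a third of the planned deaths, in a 130-patient phase II trial that needs its precision. The proposed level is silent in 79-86% of trials at the planned effect, and the documents give no source for hazard ratios of 2.0 or 2.5. A DSMB seeing an observed ratio above about 2.2 hardly needs a printed threshold, and a strict level might reassure wrongly at 1.9. Missed or late transplant, one feared route to harm, is already checked every five patients when CPX-attributed.

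Much of this stands: it keeps the gain small at the planned effect and makes the level a matter of judgement. It does not remove the point. A pause for review is neither a boundary nor a conclusion, the DSMB's discretion below the level is untouched, and the plan already uses numeric suspend-and-review triggers for toxicity.

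A reader might infer that the plan leaves the DSMB unable to see or act on harm, or that no level exists anywhere. The documents do not support either. Section 17.5 sends other considerations to the DSMB, and neither a DSMB charter nor the institutional monitoring plan cited in Section 15.0 is among the documents reviewed. The most that can be said is that this protocol states no level.

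**Conclusion.** The point holds as a cheap improvement, not as an error in the plan. Conditional power under Section 17.5 serves its futility purpose, but it rises from no difference through harm to Arm B and so cannot signal that harm. The direction rests on Section 17.3 favouring transplant and held under all three readings, at the alpha levels tried and at both drifts; had the unseen curves favoured Arm B it would reverse, which the text does not suggest. It should not be read as rising at every step towards worse Arm B survival, since it climbs back when Arm B looks much better.

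The sizes are illustrative. They rest on substitute curves, alpha .05 for conditional power, assumed stratum effects and a chosen pause level. The benefit is small at the planned effect and lies mainly in protection against larger harm. Confidence is medium.

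**What to change.** Add to Section 17.5:

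> *At the same interim analysis the DSMB will receive deaths by arm, the OS hazard ratio and the stratified log-rank statistic. If Arm B survival is worse at one-sided p<0.005, randomization will be paused pending DSMB review, regardless of conditional power; the DSMB may recommend resuming, and a pause is not a trial conclusion or a rejection of the null.*

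The level is illustrative, for the sponsor and DSMB to settle. If a charter already sets one, a cross-reference is enough. The pause follows the analysis, so it does not conflict with accrual continuing while the analysis is done.

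The cost is a short paragraph and one table at a look already planned. The downsides are about a 0.3-0.5% chance of an unnecessary pause if the arms are equal, and some loss of precision if the trial then stops. Sample size is unchanged, and so is final alpha while a pause is not counted as a rejection. If a pause were reported as a result, the one-sided error towards CPX-351 being worse would go from 2.1-3.0% to 2.4-3.4%, which is why the last clause matters.

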18.0 INVESTIGATOR OBLIGATIONS

The PI is responsible for the conduct of the clinical trial at the site and is responsible for personally overseeing the treatment of all study subjects. The PI must assure that all study site personnel, including sub-Investigators and other study staff members, adhere to the study protocol and to all applicable regulations and guidelines regarding clinical trials both during and after study completion.

All subjects are informed of the nature of the program, its possible hazards, and their right to withdraw at any time, and each subject signs a form indicating their consent to participate prior to receiving any study-related procedures.

19.0 ADMINISTRATIVE AND REGULATORY CONSIDERATIONS

19.1 Documentation

The documentation of clinical data must be stored by the Sponsor according to legal requirements. The PI and study staff has responsibility for maintaining a comprehensive and centralized filing system containing all study-related documentation. These files must be suitable for inspection by the Sponsor, the FDA, and/or other applicable regulatory agencies/competent authorities at any time, and should consist of the following elements: subject files (complete medical records, laboratory data, supporting source documentation, and the Informed Consent); study files (the protocol with all amendments, copies of all pre-study documentation, and all correspondence between the Competent Authorities, IRB/EC, site, and Sponsor); and drug accountability files, containing a complete account of the receipt and disposition of the study drug.

19.2 Data Collection

Research data will be recorded in a study-specific, password protected database using a unique study ID for each patient to assure patient confidentiality. Data from source documents will be transcribed into this database. Source documents are documents where patient data are recorded and documented for the first time. They include, but are not limited to, hospital records, clinical and office charts, laboratory notes, memoranda, quality of life assessments, pharmacy dispensing records, recorded data from automated instruments, copies of transcriptions that are certified after verification as being accurate and complete, X-rays, patient files, and records kept at the pharmacy, laboratories, and medico-technical departments involved in the clinical trial. There will be no case reports forms (CRFs) used for this trial.

19.3 Protocol Interpretation and Compliance

The procedures defined in the protocol are carefully reviewed by the PI, co-investigators and study staff prior to the time of study initiation to ensure accurate representation and implementation. Protocol amendments, if any, are reviewed and implemented promptly following IRB/EC and relevant Competent Authorities approval.

19.4 Disclosure of Data/Publication

The results of this clinical trial may be used for public dissemination in the form of papers, abstracts, posters, or other informational materials to be presented at scientific meetings, or published in professional journals, or as a part of an academic thesis by an investigator. Identifiable patient data may not be used for any of these presentations, manuscripts, or reports unless directed by law.

19.5 Ethical Considerations

Each named Investigator agrees to conduct this study in accordance with applicable United States clinical trial regulations and guidelines, the ICH (E6) GCP guidelines, the IRB/EC and local legal requirements and with the Declaration of Helsinki (1989). The Investigator will conduct all aspects of this study in accordance with all national, state, and local laws of the applicable regulatory agencies.

19.6 Informed Consent

Per local institutional policies/guidelines, the PI, sub-Investigators and qualified designees assume the responsibility of obtaining written Informed Consent for each subject or the subject's legally authorized representative before any study-specific procedures are performed. Subjects meeting the criteria set forth in the protocol will be offered the opportunity to participate in the study. To avoid introduction of bias, the Investigator must exercise no selectivity with regard to offering eligible subjects the opportunity to participate in the study.

Subjects or legal guardians of all candidate subjects will receive a comprehensive explanation of the proposed treatment, including the nature of the therapy, alternative therapies available, any known previously experienced adverse reactions, the investigational status of the study drug, and other factors that are part of obtaining a proper Informed Consent. Subjects will be given the opportunity to ask questions concerning the study, and adequate time to consider their decision to or not to participate. Informed Consent will be documented by the use of a written Consent Form that includes all the elements required by FDA regulations and ICH guidelines. The form is to be signed and dated by the subject and by the person who administers the consent process. The original signed Consent Form will be filed in the research record. One copy of the signed form will be given to the patient; another copy will be filed in the patient's medical record.

If an amendment to the protocol changes the subject participation schedule in scope or activity, or increases the potential risk to the subject, the Informed Consent Form must be amended. The revised Informed Consent Form must be used to obtain re-consent from any subjects currently enrolled in the study if the subject is affected by the amendment (as determined by the PI or designee) and must be used to document consent from any new subjects enrolled after the approval date of the amendment.

19.7 Institutional Review Board/Ethics Committee

The PI will assure that an appropriately constituted IRB/EC that complies with the requirements of 21 CFR Section 56 or written assurance of compliance with ICH (E6) guidelines will be responsible for the initial and continuing review and approval of the clinical study. Before initiation of the study, the PI or designee will forward copies of the protocol and Consent Form to be used for the study to the IRB/EC for its review and approval. The PI or designee will also assure that all changes in the research activity and all unanticipated problems involving risks to human subjects or others will be reported promptly to the IRB/EC, and that no changes will be made to the protocol without prior IRB/EC approval, except where necessary to eliminate apparent immediate hazards to human subjects. The Investigator or designee will be responsible for submitting periodic progress reports to the IRB/EC at intervals appropriate to the degree of subject risk involved in the study, but not less than once per year and at the completion or termination of the study.

19.8 Subject Privacy

The Sponsor and the Investigator affirm and uphold the principle of the subject's right to privacy. The Sponsor, its designees, and the Investigator shall comply with applicable national and local privacy laws.

To verify compliance with this protocol, the Sponsor, or its designee, will require that the Investigator permit the Sponsor, or its designee's monitor to review the subject's original medical records. Should access to such medical records require a waiver or authorization separate from the statement of Informed Consent, the Investigator will obtain such permission in writing from the subject before the subject is entered into the study.

20.0 STOPPING THE STUDY

The Principal Investigator reserves the right to terminate this study at any time.

22.0 APPENDICES

Appendix A: Karnofsky Performance Status Scale

Appendix B: Acute GVHD Grading Scale

Appendix C: Chronic Graft-Versus-Host Disease Grading

Appendix D: Potential adverse events associated or expected with hematopoietic cell transplantation

22.1 APPENDIX A: Karnofsky Performance Status Scale

General	Index	Specific Criteria
Able to carry on normal activity; no special care needed	100	Normal, no complaints, no evidence of disease
	90	Able to carry on normal activity, minor signs or symptoms of disease
	80	Normal activity with effort, some signs or symptoms of disease
Unable to work, able to live at home and care for most personal needs, varying amount of assistance needed	70	Care for self, unable to carry on normal activity or to do work
	60	Requires occasional assistance from others but able to care for most needs
	50	Requires considerable assistance from others and frequent medical care
Unable to care for self, requires institutional or hospital care or equivalent; disease may be rapidly progressing	40	Disabled; requires special care and assistance
	30	Severely disabled, hospitalization indicated, death not imminent
	20	Very sick, hospitalization necessary, active supportive treatment necessary
	10	Moribund
	0	Dead

